Wear and Replacement Schedules	Wear Schedule: The Test lenses are used as daily wear. One of the Test lenses will be reusable, cleaned and stored each night and the other will be daily disposable with a new lens worn each day. Replacement Schedule: The Test and/or Control lenses that is fit at Visit 1 will be replaced at Visit 2 optimization visit and then worn as daily reusable modality without further planned replacement for 7 ± 1 day. There will be a 7 ± 3 day wash-out period before the remaining lens is fit, and the procedures are repeated. The test lenses will also be replaced when lost or damaged.
Objectives	This study is an evaluation of the lens fit and handling response of both the Air Optix® multifocal contact lenses Plus HydraGlyde and the Dailies Total 1® multifocal contact lens.
Study Endpoints	Primary endpoints: Lens centration and lens movement Secondary endpoints: Lens handling Other observations: number of lenses needed to fit (optimize) the subject, visual acuity and subjective responses.
Study Design	This is a single-masked, randomized-controlled, dispensing clinical trial. A total of approximately 40 eligible hyperopic and myopic subjects will be targeted to complete the study. The subjects will be fit in the first study lens based on the randomization scheme and wear the lens for 3 ± 1 day then undergo optimization, if applicable, and wear the optimized pair with a follow-up in 7 ± 1 day. The remaining lens will be fit according to the random scheme at Visit 4 following a 7 ± 3 day wash-out period. The procedures will be repeated for the 2 nd lens. The primary endpoints will be lens centration and lens movement.
Sample Size	A total of approximately 40 subjects will be targeted to complete.
Study Duration	The study will last approximately 2-4 months.

Anticipated Study Population	Healthy male and female volunteers with presbyopia will be invited to participate in the study. Subjects will be adapted soft contact lens wearers in both eyes. Additional information regarding the eligibility of the population can be found in the inclusion/exclusion criteria outlined below.
Eligibility Criteria	
Potential subjects must satisfy all the following criteria to be enrolled in the study
 
 1. The subject must read, understand, and sign the STATEMENT OF INFORMED CONSENT and receive a fully executed copy of the form. 2. The subject must appear able and willing to adhere to the instructions set forth in this clinical protocol. 3. The subject must be between 40 and 70 years of age (inclusive). 4. The subject's distance spherical equivalent refraction must be in the range of +1.25 D to +3.75 D or -1.25 D to -4.00 D in each eye. 5. The subject's refractive cylinder must be \leq0.75 D in each eye. 6. The subject's ADD power must be in the range of +0.75 D to +2.50 D. 7. The subject must have best corrected visual acuity of 20/20³ or better in each eye. 8. Subjects must own a wearable pair of spectacles if required for their distance vision. 9. The subject must be an adapted soft contact lens wearer in both eyes (i.e. worn lenses a minimum of 2 days per week for at least 8 hours per wear day, for 1 month of more duration). 10. The subject must either already be wearing a presbyopic contact lens correction (e.g., reading spectacles over contact lenses, multifocal or monovision contact lenses, etc.) or if not respond positively to at least one symptom on the "Presbyopic Symptoms Questionnaire". 
Potential subjects who meet any of the following criteria will be excluded from participating in the study:
 
 1. Currently pregnant or lactating. 2. Any active or ongoing ocular or systemic allergies that may interfere with contact lens wear. 3. Any active or ongoing systemic disease, autoimmune disease, or use of medication, which may interfere with contact lens wear. This may include, but not be limited to, diabetes, hyperthyroidism, Sjögren's syndrome, xerophthalmia, acne rosacea, Stevens-Johnson

	
syndrome, and immunosuppressive diseases or any infectious diseases (e.g. hepatitis, tuberculosis).
 
 4. Clinically significant (Grade 3 or 4) corneal edema, corneal vascularization, corneal staining, tarsal abnormalities or bulbar injection, or any other corneal or ocular abnormalities which would contraindicate contact lens wear. 5. Entropion, ectropion, extrusions, chalazia, recurrent styes, dry eye, glaucoma, history of recurrent corneal erosions. 6. Any previous, or planned, ocular or intraocular surgery (e.g. radial keratotomy, PRK, LASIK, lid procedures, dacryocystorhinostomy, cataract surgery, retinal surgery, etc.). 7. A history of amblyopia, strabismus or binocular vision abnormality. 8. Any current ocular infection or inflammation. 9. Any current ocular abnormality that may interfere with contact lens wear. 10. Use of any of the following oral medications within 1 week prior to enrollment: oral retinoid isotretinoin (e.g. Accutane), oral tetracyclines, topical scopolamine, oral antihistamines (e.g., Chlor-Trimeton, and Benadryl), systemic steroids. 11. Use of any ocular medication, with the exception of rewetting drops. 12. History of herpetic keratitis. 13. Participation in any contact lens or lens care product clinical trial within 7 days prior to study enrollment. 14. Employee or immediate family member of an employee of clinical site (e.g., Investigator, Coordinator, Technician). 15. Any known hypersensitivity or allergic reaction to OPTI-FREE® Puremoist® multi-purpose care solution, sodium fluorescein or single-use preservative free rewetting drop solution.
Disallowed Medications/Interventions	Use of any prescription or over-the-counter (OTC) medications that may affect contact lens wear.
Measurements and Procedures	logMAR Visual acuity and Subjective responses for vision using the CLUE questionnaire.
Microbiology or Other Laboratory Testing	None

Study Termination	The occurrence of one or more Unanticipated Adverse Device Effect (UADE), or any SAE where relationship to study agent cannot be ruled out, will result in stopping further dispensing investigational product. In the event of a UADE or SAE, the Sponsor Medical Monitor may unmask the treatment regimen of subject(s) and may discuss this with the Principal Investigator before any further subjects are enrolled.
Ancillary Supplies/ Study-Specific Materials	Rewetting drops, lens cases, glass vials, saline, ETDRS light cabinet, logMAR charts, and Near logMAR charts. OPTI-FREE® Puremoist® Contact Solution.
Principal Investigator(s) and Study Institution(s)/Site(s)	A full list of Principal Investigators, clinical sites, and institutions is kept separately from the Study Protocol and is included in the study Trial Master File.

Figure 1: Study Flowchart

COMMONLY USED ABBREVIATIONS AND DEFINITIONS OF TERMS

ADD	Plus Power Required for Near Use
ADE	Adverse Device Effect
AE	Adverse Event/Adverse Experience
BCVA	Best Corrected Visual Acuity
BSCVA	Best Spectacle Corrected Visual Acuity
CFR	Code of Federal Regulations
CLUE	Contact Lens User Experience
COAS	Complete Ophthalmic Analysis System
COM	Clinical Operations Manager
CRA	Clinical Research Associate
CRF	Case Report Form
CRO	Contract Research Organization
CT	Center Thickness
	
D	Diopter
DMC	Data Monitoring Committee
eCRF	Electronic Case Report Form
EDC	Electronic Data Capture
ETDRS	Early Treatment Diabetic Retinopathy Study
FDA	Food and Drug Administration
GCP	Good Clinical Practice
HIPAA	Health Insurance Portability and Accountability Act
IB	Investigator's Brochure
ICF	Informed Consent Form
ICH	International Conference on Harmonization
IDE	Investigational Device Exemption
IEC	Independent Ethics Committee
IRB	Institutional Review Board
ISO	International Organization for Standardization
ITT	Intent-to-Treat
JJVC	Johnson & Johnson Vision Care, Inc.
LC	Limbus Center
LogMAR	Logarithm of Minimal Angle of Resolution
MedDRA [®]	Medical Dictionary for Regulatory Activities
MOP	Manual of Procedures
NIH	National Institutes of Health
OD	Right Eye
OHRP	Office for Human Research Protections
OHSR	Office for Human Subjects Research
OS	Left Eye
OU	Both Eyes
PD	Protocol Deviation
PHI	Protected Health Information
PI	Principal Investigator
PIG	Patient Instruction Guide

PQC	Product Quality Complaint
PRO	Patient Reported Outcome
QA	Quality Assurance
QC	Quality Control
SAE	Serious Adverse Event/Serious Adverse Experience
SAP	Statistical Analysis Plan
SAS	Statistical Analysis System
SD	Standard Deviation
SOP	Standard Operating Procedure
UADE	Unanticipated Adverse Device Effect
USADE	Unanticipated Serious Adverse Device Effect
VA	Visual Acuity

1. INTRODUCTION AND BACKGROUND

Competitors have launched multifocal lenses that have the same optical design but are manufactured in different silicone hydrogel materials. The optical designs are center near aspheric. For aspheric designs the mechanical fit of the lens, centration in particular, can have a significant impact on the optical performance of the lens. The purpose of this study is to evaluate two such designs, Air Optix® multifocal contact lenses Plus HydraGlyde® manufactured in lotrafilcon B and Dailies Total 1® manufactured in deleficon-A, and compare their mechanical fitting characteristics.

1.1. Name and Descriptions of Investigational Products

Test Lenses: J Dailies Total 1® multifocal contact lenses manufactured in deleficon A. Air Optix® multifocal contact lenses Plus HydraGlyde® manufactured in lotrafilcon B

1.2. Intended Use of Investigational Products

All lenses are intended to correct spherical refractive error and presbyopia. For this study one of the lenses is intended to be used as a daily wear, reusable lens. These lenses will be cleaned, disinfected and stored in multipurpose lens solutions. The second test lens will be worn as a daily disposable lens, with the lenses being discarded after a day of wear. The Lens systems will be fit in a randomized fashion. After fitting, each subject will return for an optimization visit and then a follow-up. The sequence will then be repeated with the additional study lens type. Each study lens type will be worn for a total of approximately 8-12 days.

1.3. Summary of Findings from Nonclinical Studies

Not Applicable

1.4. Summary of Known Risks and Benefits to Human Subjects

Anticipated risks and adverse reactions with this lens are similar to those with other soft daily wear contact lenses used to correct presbyopia. A listing of examples of adverse reactions is found in the Section 13 of this protocol. The investigator should follow normal clinical guidelines regarding examination and care of subjects who participate in this trial. Refer to study lens package insert for additional details. The study multifocal contact lens is designed for the correction of refractive spherical ametropia and presbyopia. one study contact lenses is manufactured in lotrafilcon B and will be worn in a daily wear, reusable modality. The other study contact lens is manufactured in deleficon A and will be worn in a daily wear, disposable modality. These lens is not intended for extended wear in this study.

1.5. Relevant Literature References and Prior Clinical Data Relevant to Proposed Clinical Study

Information about both the Air Optix® Plus HydraGlyde® Multifocal Contact Lenses and Dailies Total 1® Multifocal Contact Lenses may be found in the package inserts.

2. STUDY OBJECTIVES, ENDPOINTS AND HYPOTHESES

2.1. Objectives

This study is an evaluation of the lens fit and handling response of both the Air Optix® multifocal contact lenses Plus HydraGlyde and the Dailies Total 1® multifocal contact lens.

2.2. Endpoints

Primary endpoints: lens centration and lens movement

Secondary endpoints: Subjective lens handling

Other observations: number of lenses needed to fit (optimize) the subject, visual acuity and subjective responses.

2.3. Hypotheses

The following hypotheses will be tested throughout this investigation.

Primary Hypotheses:

1. After 6-8 days of wear in the optimized lenses, the proportion of lenses graded as being centered for the test lens will be non-inferior compared to the control lens. A non-inferiority margin of 0.67 odds ratio will be used.
2. After 6-8 days of wear in the optimized lenses, the proportion of lenses graded as having optimal lens movement in primary gaze for the test lens will be non-inferior compared to the control lens. A non-inferiority margin of 0.67 odds ratio will be used.

Secondary Hypothesis:

1. After 6-8 days of wear in the optimized lenses, the overall lens handling of the test lens system will be non-inferior compared to that of the control lens system. A non-inferiority margin of -5 CLUE points will be used.

3. TARGETED STUDY POPULATION

3.1. General Characteristics

Healthy male and female subjects who are habitual soft contact lens wearers will be recruited. Subjects will be at least 40 years of age and not older than 70 years of age. They will be hyperopic or myopic and have presbyopia.

3.2. Inclusion Criteria

Potential subjects must satisfy all the following criteria to be enrolled in the study:

1. The subject must read, understand, and sign the STATEMENT OF INFORMED CONSENT and receive a fully executed copy of the form.
2. The subject must appear able and willing to adhere to the instructions set forth in this clinical protocol.
3. The subject must be between 40 and 70 years of age (inclusive).
4. The subject's distance spherical equivalent refraction must be in the range of +1.25 D to +3.75 D or -1.25 D to -4.00 D in each eye.
5. The subject's refractive cylinder must be \leq 0.75 D in each eye.
6. The subject's ADD power must be in the range of +0.75 D to +2.50 D.
7. The subject must have best corrected visual acuity of 20/20³ or better in each eye.
8. Subjects must own a wearable pair of spectacles if required for their distance vision.
9. The subject must be an adapted soft contact lens wearer in both eyes (i.e. worn lenses a minimum of 2 days per week for at least 8 hours per wear day, for 1 month of more duration).
10. The subject must either already be wearing a presbyopic contact lens correction (e.g., reading spectacles over contact lenses, multifocal or monovision contact lenses, etc.) or if not respond positively to at least one symptom on the "Presbyopic Symptoms Questionnaire".

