3.3. Exclusion Criteria

Potential subjects who meet any of the following criteria will be excluded from participating in the study:

1. Currently pregnant or lactating.
2. Any active or ongoing ocular or systemic allergies that may interfere with contact lens wear.
3. Any active or ongoing systemic disease, autoimmune disease, or use of medication, which may interfere with contact lens wear. This may include, but not be limited to, diabetes, hyperthyroidism, Sjögren's syndrome, xerophthalmia, acne rosacea, Stevens-Johnson syndrome, and immunosuppressive diseases or any infectious diseases (e.g. hepatitis, tuberculosis).
4. Clinically significant (Grade 3 or 4) corneal edema, corneal vascularization, corneal staining, tarsal abnormalities or bulbar injection, or any other corneal or ocular abnormalities which would contraindicate contact lens wear.
5. Entropion, ectropion, extrusions, chalazia, recurrent styes, dry eye, glaucoma, history of recurrent corneal erosions.
6. Any previous, or planned, ocular or intraocular surgery (e.g. radial keratotomy, PRK, LASIK, lid procedures, dacryocystorhinostomy, cataract surgery, retinal surgery, etc.).
7. A history of amblyopia, strabismus or binocular vision abnormality.
8. Any current ocular infection or inflammation.
9. Any current ocular abnormality that may interfere with contact lens wear.
10. Use of any of the following oral medications within 1 week prior to enrollment: oral retinoid isotretinoin (e.g. Accutane), oral tetracyclines, topical scopolamine, oral antihistamines (e.g., Chlor-Trimeton, and Benadryl), systemic steroids.

11. Use of any ocular medication, with the exception of rewetting drops.
12. History of herpetic keratitis.
13. Participation in any contact lens or lens care product clinical trial within 7 days prior to study enrollment.
14. Employee or immediate family member of an employee of clinical site (e.g., Investigator, Coordinator, Technician).
15. Any known hypersensitivity or allergic reaction to OPTI-FREE® Puremoist® multi-purpose care solution, sodium fluorescein or single-use preservative free rewetting drop solution.

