4. STUDY DESIGN AND RATIONALE

4.1. Description of Study Design

The clinical study is a randomized-controlled, single-masked, crossover clinical trial. There are two study treatments. A total of approximately 50 subjects will be enrolled with 40 (20 myopic and 20 hyperopic) eligible subjects targeted to complete the study. The first Test article will be dispensed for 3 ± 1 day and an optimization visit will occur. The final lens pair will be dispensed for 7 ± 1 day and the at the follow-up the final lens measurements will occur. Subjects will complete a 7 ± 3 days washout between each fitting. The second study lens will then be fit and follow the same sequence as the first lens.

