4.2. Study Design Rationale

The study is intended to compare two study lens types and the initial performance, in terms of the mechanical lens fit and handling after a period of lens dispensing. The lenses are dispensed to determine the handling responses and the comparison is made after a total of 8-12 days of wear.

The crossover study design was chosen to control for variables that may impact the lens performance between subjects. A washout period between Period 1 and Period 2 of wear is used to minimize the chance of carryover effect in the study data.

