5.2. Masking

This is a single-masked study with the subjects being masked. The masking will be partial as the subjects will have different wear modalities however the brand name of the lenses will not be revealed to the subject.

Under normal circumstances, the mask should not be broken until all subjects have completed the study and the database is finalized. Otherwise, the mask should be broken only if specific emergency treatment/course of action would be dictated by knowing the treatment status of the subject. In such cases, the Investigator may, in an emergency, contact the medical monitor. In the event the mask is broken, the Sponsor must be informed as soon as possible. The date, time, and reason for the unmasking must be documented in the subject record. The Investigator is also advised not to reveal the study treatment assignment to the clinical site or Sponsor personnel.

Subjects who have had their treatment assignment unmasked are expected to return for all remaining scheduled evaluations. Subjects who are discontinued may be replaced.

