3.10	Lens Fit Assessment:	
Evaluate and grade lens centration, primary gaze movement, upgaze movement and tightness (push-up test).
 
 • The subject should not proceed to wear the lenses if any of the following is observed: • presence of limbal exposure (appearance of clear cornea) in any gaze • presence of edge lift • presence of unacceptable movement 	

		
(excessive or insufficient) in all three movement categories (primary gaze, upgaze, and push-up).
 
If either lens is deemed unacceptable, the subject will be discontinued from the study. Remove the lenses, perform a slit-lamp evaluation, and complete the Final Evaluation form.
	
3.11	Collection of unworn lenses (if applicable)	
If the first lens type fit on the subject was the daily disposable lenses collect unworn lenses returned by the subject.
	
3.12	Lens Removal	
Have the subject remove the study lenses and store in saline in a labeled glass vial.
 
Note: Lenses do not need to be stored in a refrigerator.
	
3.13	Biomicroscopy	
Perform biomicroscopy OD and OS. Slit Lamp Classification Scales will be used to grade the findings.
 
For the conjunctival redness [REDACTED] 0.5 unit increments will be used in the grading.
 
Corneal Staining Assessment [REDACTED] will be graded in 1.0 increments.
 
If the clearance of the fluorescein needs to be expedited, preservative-free rewetting drops or saline may be instilled.
	[REDACTED] [REDACTED] [REDACTED]
3.14	Distance and Near Exit Visual Acuity	
Distance and near Snellen visual acuity will be measured for each eye with the subject's habitual correction in place.
 
For near measures use the ETDRS 2000 Series Chart 1 or 2. The acuity will be recorded to the nearest letter OD, OS and OU.
	[REDACTED]
3.15	Schedule Follow-up	
The subject will be scheduled to return for their next appointment in 7 ± 3 days.
 
NOTE: Subject may wear their habitual spectacles or contact lenses during the washout period.
	

VISIT 4

The subjects may present to Visit 4 wearing their habitual spectacles or contact lenses, if required for their distance vision.

Visit 4: Baseline Treatment 2		
Step	Procedure	Details
4.1	Adverse Events and Concomitant Medications Review	
Review the subject's concomitant medications and record any changes from the previous study visit.
 
Record any adverse events or medical history changes from the previous study visit.

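### Habitual wearers of either study lens are eligible and may wear it between periods, which can bias the Test–Control contrast, mainly for CLUE handling

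*Combined protocol and SAP*

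**What the plan says.** **Eligibility.** Criterion 9 of section 3.2 requires that "The subject must be an adapted soft contact lens wearer in both eyes", and criterion 10 names multifocal lenses among the accepted current corrections: "The subject must either already be wearing a presbyopic contact lens correction (e.g., reading spectacles over contact lenses, multifocal or monovision contact lenses, etc". No brand is carved out. Of the 15 exclusions in 3.3, the nearest one concerns recent trials, not habitual lenses: "Participation in any contact lens or lens care product clinical trial within 7 days prior to study enrollment".

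**The lenses.** Section 1 opens: "Competitors have launched multifocal lenses that have the same optical design but are manufactured in different silicone hydrogel materials". Appendix C holds the package inserts of both products.

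**Between periods.** Section 4.1 states "Subjects will complete a 7 ± 3 days washout between each fitting", and 4.2 gives the purpose: "A washout period between Period 1 and Period 2 of wear is used to minimize the chance of carryover effect in the study data". Step 3.15 in section 7.2 then adds: "Subject may wear their habitual spectacles or contact lenses during the washout period". The introduction to Visit 4 lets subjects arrive in those lenses.

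**Masking.** Only subjects are masked. Section 5.2 calls the masking partial because the wear modalities differ, but says "the brand name of the lenses will not be revealed to the subject". Section 6.4 provides an over-label.

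**Data and model.** Step 1.4 records habitual lens type and parameters. Section 5.1 stratifies by site only. Sections 14.5 and 14.6 model lens, period and their interaction, with an open list of baseline covariates that does not name habitual lens.

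**The concern.** A subject who already wears one of the two study lenses does not meet the two arms on equal terms. That subject is used to inserting, removing and (for the reusable lens) cleaning one of them. The subject may recognise it despite the over-label, and has presumably been fitted in it successfully, since adapted wear is an entry condition. None of this applies to the other lens.

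The endpoint most exposed is the secondary one, overall handling on CLUE. It is reported by the subject and judged against a margin of -5 points. Centration and movement are less exposed, through selection: people who stay in a brand tend to be those it fits. The advantage is attached to a lens, not to a period or a subject, so a crossover does not cancel it. If more subjects wear one brand than the other, the estimate moves toward that brand.

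**Working it through.** The plan states no figure on this point, so there is none to reproduce. The check has three parts.

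**1. Can such subjects enter?** All 10 inclusion and 15 exclusion criteria were read against step 1.4. A habitual wearer of Dailies Total 1 Multifocal or Air Optix plus HydraGlyde Multifocal who meets the refractive and health criteria passes them all. Section 3.4 recruits from the site's own subject database, so such wearers are a realistic part of the pool. Their number is not given.

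**2. Does the design or model remove the advantage?** Write a subject's score as subject level + period effect + lens effect, plus an amount d when the lens worn is the habitual one. Take Test minus Control within subject and average over the two sequences:

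- subject levels cancel, and with them any subject-level main effect (baseline CLUE, age, habitual brand);
- period effects cancel through the randomised order;
- what remains is the true difference + d × (fT − fC), where fT and fC are the shares of analysed subjects who habitually wear Test and Control.

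For handling, the bias is therefore d times the net share. The documents give no value for d. As an assumption only, d = 5 points (the size of the margin) gives 5 × 0.10 = 0.5 point at a net share of 10% and 5 × 0.20 = 1.0 point at 20%. Other values of d scale in proportion. The sign depends on which brand is commoner, and equal shares with equal advantage give zero.

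**3. Illustration for centration.** Inputs:

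- proportion centred 0.75 on both lenses (control proportion in 14.2), so odds 3;
- true odds ratio 1 (assumed);
- a share f of subjects, all habitual Control wearers (assumed);
- their odds of centring on Control multiplied by k = 1.5 to 3, with 0.75 kept on Test (assumed).

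Formulas: p_k = 3k/(1+3k), so p_1.5 = 4.5/5.5 = 0.818 and p_3 = 9/10 = 0.900. Control mixture P = 0.75(1−f) + p_k·f. Observed odds ratio = 3 ÷ [P/(1−P)].

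| f (of 40 completers) | k | P | odds | observed odds ratio |
|---|---|---|---|---|
| 10% (4) | 1.5 | 0.7568 | 3.112 | 0.96 |
| 10% (4) | 3 | 0.7650 | 3.255 | 0.92 |
| 20% (8) | 1.5 | 0.7636 | 3.231 | 0.93 |
| 20% (8) | 3 | 0.7800 | 3.545 | 0.85 |

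At f = 5% the range is 0.98 to 0.96, and at 30% it is 0.89 to 0.77. On the log scale, 0.846 lies ln(0.846)/ln(0.67) = 0.42 of the way from 1 to the margin, and 0.929 lies 0.18 of the way. If the affected subjects wore Test, the shift would go above 1 instead.

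These are marginal odds ratios. The mixed model in 14.5 estimates a subject-specific one, so the figures show the order of size only.

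**The case against.** Three stronger readings are tempting, and the documents do not support them.

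- **That the washout fails.** A reader might infer this because Control, say, can be worn right through it. But subjects must arrive at Visit 1 in their habitual lenses and may wear them again before Visit 4. A subject who does so enters both periods from the same state, in either sequence. Each lens is then worn about 8–12 days, with a new pair dispensed at steps 2.14 and 5.14. Nothing in the documents suggests that the lens worn in the gap changes the centration or movement of a different lens after that.
- **That masking and the fit comparison fail.** Masking is already declared partial, and fit is graded by site staff, who are not masked. Recognition by the subject therefore bears on CLUE, and even there it is an inference. Each subject still wears both lenses in random order.
- **That baseline CLUE is contaminated.** For these subjects it does score a study lens. It is one Visit 1 value per subject, however, and as a main effect it cannot shift the within-subject difference.

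The size can also be disputed. Subjects with an unacceptable fit on either lens are discontinued, and all analyses use per-protocol completers, so everyone analysed has passed a fit screen on both lenses. The two lenses share an optical design and nearly the same geometry (8.5/14.1 mm and 8.6/14.2 mm). An eye that centres well on one may centre well on the other. If habitual Control wearers were centred in 0.90 on Control and 0.85 on Test, a 20% share gives Test 0.75 × 0.8 + 0.85 × 0.2 = 0.77 and Control 0.78. The observed odds ratio is then 3.348/3.545 = 0.94, not 0.85. Wearers of the two brands also offset each other.

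These points stand, and they limit the fit concern to a modest selection effect. They do not dispose of it, because an acceptable fit is a weaker standard than a centred lens. They leave the handling concern largely untouched. The covariate lists in 14.5 and 14.6 are open, so habitual lens could be added, but a main effect would not remove an advantage tied to one lens.

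Admitting current multifocal wearers is a legitimate choice for a pilot. Section 14.2 says, though, that the data will be used to design later trials, so a bias would carry forward.

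**Conclusion.** The point holds as a conditional bias. The criteria admit habitual wearers of either study lens, the plan records who they are, and neither the design nor the analysis uses that record. For these subjects the Test–Control contrast can favour the familiar brand: mainly in handling, and less in centration and movement.

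The size is unknown because the net share of wearers is unknown. Under the stated assumptions the centration odds ratio moves from 1 to 0.96–0.92 at a 10% net share of Control wearers and to 0.93–0.85 at 20%. It moves the other way for Test wearers. With few such subjects, or balanced brands, the effect is small. With about 40 completers, 10% is four people, so balance by chance cannot be relied on.

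**What to change.** **Preferred.** Add to 3.3 and to the Synopsis an exclusion for subjects whose habitual contact lens is either study lens, checked from step 1.4 at the eligibility decision in step 1.7. State whether it extends to Air Optix Aqua Multifocal, which Appendix C lists with the same material, diameter and base curve. The cost is one line and no new data. The downside is a somewhat smaller recruitment pool, including for the 20 hyperopes that section 4.1 requires.

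**If these subjects are kept.** Pre-specify in 14.5 and 14.6 a repeat of both analyses without them, and report their number by brand. The cost is one sensitivity run and one table row. This shows the bias but does not prevent it.

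Barring the study brands during the washout alone is not a substitute. Period 1 would still start from the study brand and Period 2 would not, which adds an asymmetry that the present rule avoids.
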